1.0 Background

Aneurysmal subarachnoid hemorrhage affects 6-8/100,000 people every year⁴. In addition to the various medical comorbidities that accompany this disease, about 50% will experience angiographic narrowing of the cerebral arteries (radiographic vasospasm) and 20-30% will experience delayed ischemic neurologic deficit (DIND, formerly clinical vasospasm)¹. The onset of vasospasm is most commonly between days 4 and 14 after the hemorrhage. Patients afflicted with DIND may go on to suffer permanent neurologic deficits which can impair their quality of life or be fatal. Although there has been much advancement in the last 15-20 years in the ability to monitor and assess this condition, there has unfortunately been scarce progress in treating it effectively³.

The current mainstay of therapy is so-called hyperdynamic therapy, in which the patient's blood pressure is augmented and blood volume increased with the hope that resistance to flow can be overcome and the brain perfused². This comes with its own set of complications, such as cardiac injury and fluid overload. It is also important to note that this modality of therapy has never been validated in a randomized, controlled trial, though it is accepted as the standard of care in many institutions⁵. Patients that are refractory to medical therapy may undergo angiographic therapy with infusion of agents such as calcium-channel blockers or papaverine or in extreme cases, balloon angioplasty. Some groups, such as the Montreal Neurological Hospital, have used infusions of the drug milrinone (Hospira, Inc Lake Forest, IL) to counter cerebral vasospasm. The smooth muscle of cerebral blood vessels is rich in phosphodiesterase-III (PDE-III), making it a promising target for this drug⁶. Milrinone is currently FDA approved for the treatment of congestive heart failure as it has both vasodilatory and inotropic effects. It is thought that these same effects may be beneficial in cerebral vasospasm. Milrinone also has anti-inflammatory effects through inhibition of interleukins⁵.

Milrinone is known to be safe with a relatively low incidence of complications. The Montreal group had no patients (out of 88 presented) with complications from milrinone infusion for as long as 9 days. To date, no study has compared the current standard-of-care, hyperdynamic therapy, with milrinone in addition to standard treatment.

2.0 Rationale and Specific Aims

The goal of this study is to assess the efficacy of milrinone as an agent to treat cerebral vasospasm by adding it to standard therapy. This will take the form of a randomized, controlled trial in which patients will receive either standard hyperdynamic therapy or hyperdynamic therapy + milrinone. The primary outcome of interest will be modified Rankin Scale (mRS) at 6 months (+/- 60 days). Secondary outcomes assessed will be need for angiographic therapy, mRS at 12 months (+/- 60 days), duration of vasospasm (in days), hospital and ICU lengths of stay, side effects/complications of both modalities of therapy, milrinone dose, name and dose of drug(s) used for intra-arterial injection, number of times angiographic therapy is required, vasopressor usage, and discharge disposition.

3.1 Inclusion/Exclusion Criteria

Inclusion

- Subjects \geq 18 years of age
- Aneurysmal subarachnoid hemorrhage, proven on CT angiogram or digital subtraction angiography
- Aneurysm treated, either by endovascular embolization or surgical clip ligation
- Evidence of increased velocities on transcranial dopplers (TCDs) and/or radiographic evidence of vasospasm as seen on angiogram
- Cerebral vasospasm as demonstrated by patient's clinical exam (new focal deficit or change in mental status not attributable to any other cause)

Exclusion

- Recurrent subarachnoid hemorrhage
- Untreated ruptured aneurysm, for any reason
- Patients who die prior to treatment for aneurysm
- Patients who are not able to complete at least 6 months of follow-up
- Patients who are admitted already in vasospasm (i.e. a delayed admission)
- Creatinine clearance less than 20 ml/min
- Women with a positive pregnancy test or who are lactating
- Other comorbidity which may adversely affect patient outcome, at the discretion of the principal investigator

4.0 Enrollment/Randomization

Location: IU Health Methodist Hospital, [name]

Process: Patients diagnosed with aneurysmal subarachnoid hemorrhage will be identified at the time of diagnosis and the research team will be contacted by the admitting team to monitor the patient. The patients will be consented and enrolled into the study as soon as possible following surgery or endovascular intervention, if the PI (or his assigned designee) determines the patient to meet all criteria other than evidence of vasospasm. A subject ID number, which is arbitrary, will be assigned to the patient once consented so that patient confidentiality may be protected. They will not, however, be randomized at this point. The patient's Legally Authorized Representative (LAR) will be contacted for consent if the patient is unable to provide it. If a LAR is not present at the bedside, initial contact may take place over the phone to establish a time to discuss the study and obtain consent in person. At the time of diagnosis of clinical vasospasm, the treating physician(s) will notify the research team. At this time, eligibility will again be reviewed with the PI (or his assigned designee) and the protocol orders will be signed and scanned to the pharmacy where they will be entered into CERNER and the pharmacy will randomize the patient to standard hyperdynamic therapy with placebo (normal saline) or standard therapy + milrinone. Randomization will take place at the time of protocol entry into CERNER. The diagnosis will be at the judgment of the treating physician and confirmed by the PI (or his assigned designee). Providers and patients will remain blinded to the drug. An index of which patients received the drug will be maintained by pharmacy services.

5.1 Study Procedures (see Figure 1)

Every effort will be made to initiate the protocol as soon as possible following confirmation of diagnosis and all eligibility criteria and to deliver the drug or placebo to the patient within two hours of order placement/protocol initiation. Diagnosis of clinical vasospasm will be at the

discretion of the treating physician or practitioner, and verified by the PI (or his assigned designee). The pharmacy services will then randomize the patient to receive either milrinone or placebo (normal saline). All patients will undergo treatment per the institutional protocol, which is to infuse fluids (crystalloid or colloid) at an increased rate to maintain a central venous pressure greater than 8 mmHg and progressive increase in blood pressure either by removing antihypertensive medications or using vasopressors, with the addition of milrinone or placebo based on randomization. Standard protocol in our institution calls for progressive increase of systolic pressure until symptoms subside, up to 220 mmHg. All patients will receive an infusion of milrinone or placebo at 0.75 mCg/kg/min. If no improvement is noted within 24 hours, the infusion will be increased to 1.25 mCg/kg/min. All patients in both groups will receive the same infusion at the same rate with the same parameters for increase of dose and for weaning (see below). The drug will be ordered by the physician and provided by pharmacy services in the standard institutional preparation. These parameters are the same as those used at the Montreal Neurological Hospital.

Once the patient is randomized in the study, they will continue to undergo TCDs on a three times per week basis as per institutional protocol. This number, along with the patient's clinical status, will be followed until symptoms resolve. Angiographic therapy may be utilized as needed based on the patient's needs and judgment of the treating physician. If no symptoms are evidenced for 72 hours, then the milrinone/placebo infusion will be weaned at a rate of 0.25 mCg/kg/min every 24 hours until a rate of 0.25 mCg/kg/min is reached, then the infusion will be turned off after 24 hours at this rate. For patients receiving an initial dose of 0.25 mCg/kg/min and titrated up to 0.375 mCg/kg/min, the infusion will be weaned to 0.125 mCg/kg/min for 24 hours then turned off. The weaning will not occur at a rate faster than 0.75 mCg/kg/min over 72 hours. HHH therapy will be weaned according to the standard institutional protocol. If symptoms recur, the protocol will be restarted. Patients with severe, refractory symptoms may still undergo angiographic rescue therapy. Special dosing will be followed for patients with impaired renal function, based on creatinine clearance (CrCl), checked at some point during the current hospital admission and prior to study drug initiation. This will be as follows:

CrCl (mL/min)	Initial Dose	Titration Dose
Greater than 50 mL/min	0.75 mCg/kg/min	1.25 mCg/kg/min
41- 50 mL/min	0.5 mCg/kg/min	0.75 mCg/kg/min
31-40 mL/min	0.375 mCg/kg/min	0.5 mCg/kg/min
21-30 mL/min	0.25 mCg/kg/min	0.375 mCg/kg/min

Table 1 – Renal dosing parameters

This dosing schema is reflective of the Montreal protocol⁵. While the initial dose of 0.75 mcg/kg/min is less than the currently maximum approved dose of 1.13 mcg/kg/min for congestive heart failure, the maximum titration dose of 1.25 mcg/kg/min is above this. The Montreal group presented 88 patients who were given this same dosing titration with minimal side effects⁵, so the investigators believe this procedure to be safe.

Data will be collected and entered into the study database. See Appendix A for a list of data points that will be collected. mRS collection will be carried out at follow-up appointments in the office or over the phone depending on patient availability.

The infusion of the drug may pose risks, including hypotension, arrhythmias, tachycardia, chest pain, and headache. In a very small number of cases, patients may develop severe arrhythmias

or anaphylaxis if allergic to the compound or an ingredient in the preparation. Any patients with low blood pressure will be treated with increased rates of intravenous (IV) fluids and vasoconstrictor agents to raise the blood pressure. This is standard of care for patients suffering from vasospasm already. At the discretion of the treating provider, any patients with dangerously low blood pressure, or other symptoms of shock, will have milrinone/placebo discontinued, however, their data will still be used in final analysis. Final outcome data will also still be collected on these patients.

Angiographic therapy may include:

- Diagnostic angiogram (using dye in the artery to look at blood flow in the brain)
- Use of medications injected into the arteries to dilate the arteries and relieve spasm
- Use of a balloon to dilate parts of the artery that are very tight.

The type of angiographic therapy that is used will be at the discretion of the treating provider. This is standard of care for patients with subarachnoid hemorrhage.

Women of childbearing age will receive a urine pregnancy test when they present to the hospital/emergency room as standard of care. This will occur prior to being approached by the research team.

6.0 Reporting of Adverse Events or Unanticipated Problems involving Risk to Participants or Others

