Appendix A – Data Points for Milrinone Protocol

➤ **Demographics**

- Name
- DOB
- Age
- MRN
- Study ID#
- Gender
- Ethnicity
- Race

➤ **Past Medical History**

- HTN
- Smoker

➤ **Presentation/Pre-Intervention Data**

- Date of SAH symptom onset
- Date of hospital admission
- Time of hospital admission
- Hunt/Hess score on admission
- Fischer score on admission
- Location of aneurysm (side and vessel)
- Size of aneurysm
- # of aneurysms
- Modality of treatment indicated (clip/coil/both)
- Date of treatment procedure
- Time of treatment procedure

➤ **Post-Intervention Data**

- First date of elevated TCD
- Time of first elevated TCD
- Measurement of first elevated TCD
- Severity of spasm
- Mean TCD throughout hospitalization
- Max TCD throughout hospitalization
- Need for EVD
- Date of clinical diagnosis of vasospasm
- Time of clinical diagnosis of vasospasm
- Duration of spasm
- Date of end of spasm
- Evidence of ischemic changes on CT prior to study drug initiation (date/time)
- Evidence of ischemic changes on CT any time during hospitalization (date/time)
- Vasopressor usage
 - Drug(s) used
 - Duration of use

➤ **Study Drug Data**

- Date study drug initiated
- Time study drug initiated
- Duration of study drug exposure
- Study drug dose at initiation
- Was study drug titrated up?

- Hemodynamic parameters
- Creatinine clearance checked during current admission prior to study drug initiation
- Was study drug discontinued early due to complications?

➤ **Angiographic Therapy Data**

- Results of angiogram
- Severity of spasm on angiogram
- Intra-arterial drug use?
- Number of times angiographic therapy required

➤ **Complications**

- Hypotension
- Tachycardia
- Arrhythmias
- Chest pain
- Others at discretions of provider

➤ **Outcomes**

- Length of ICU stay
- Date of transfer to floor
- Date of discharge
- Length of hospital stay
- Discharge disposition
- Modified Rankin Score at 6 months
- Modified Rankin Score at 12 months
- Whether patient received milrinone or placebo

Figure 1

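### Table 1 sets the dose by creatinine clearance, but a value from any point in the admission suffices, so titration, a restart or even the first dose can use a band that no longer applies

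*Combined protocol and SAP*

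**What the plan says.** Section 5.1 bases dosing in renal impairment on CrCl. In mcg/kg/min, Table 1 gives these initial and titration rates:

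- CrCl above 50 mL/min: 0.75, then 1.25
- 41–50: 0.5, then 0.75
- 31–40: 0.375, then 0.5
- 21–30: 0.25, then 0.375

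The CrCl that selects the row is one "checked at some point during the current hospital admission and prior to study drug initiation". No maximum age is set.

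The two later dosing decisions rest on symptoms alone. For titration the standard-dose rule is "If no improvement is noted within 24 hours, the infusion will be increased to 1.25 mCg/kg/min". For recurrence it is "If symptoms recur, the protocol will be restarted".

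Renal function comes up in two other places. Section 3.1 excludes "Creatinine clearance less than 20 ml/min". Section 4.0 has eligibility reviewed again when clinical vasospasm is diagnosed, and section 5.1 adds "Every effort will be made to initiate the protocol as soon as possible following confirmation of diagnosis and all eligibility criteria". Neither of these steps calls for a new measurement.

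Appendix A lists one renal item: "Creatinine clearance checked during current admission prior to study drug initiation". It also lists the dose at initiation, whether the drug was titrated up and the duration of exposure. It has no item for a later CrCl or for a restart.

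**The concern.** Consent is sought soon after the aneurysm is treated, while dosing waits for clinical vasospasm, which section 1.0 places most commonly on days 4 to 14 after the haemorrhage. A CrCl taken on admission can therefore be many days old at the first dose and older at each later step, and it still meets the wording. If renal function has declined meanwhile, staff who follow the plan exactly will use the wrong row of Table 1, and nothing prompts them to notice. Nor does any rule say what to do if CrCl falls a band, or below the exclusion limit, while the infusion runs.

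What is at stake is the safety of patients on milrinone. Section 5.1 lists hypotension, arrhythmias and tachycardia among the infusion risks. Providers are blinded, and a moderate fall in blood pressure is to be met with fluids and vasoconstrictors, which these patients already receive for vasospasm. An excessive rate could thus be managed without anyone checking CrCl or dose. Appendix A would not let the mismatch be found afterwards.

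**Working it through.** The plan gives no calculated figure on this point to reproduce. The inputs are the Table 1 rates and the timing rules in sections 1.0 and 5.1.

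**Dose excess.** Suppose the row in use comes from an earlier CrCl and current CrCl lies in a lower band. The ratio is the rate given divided by the rate in the current band. The highest rate Table 1 permits in a band is its titration dose, so two comparisons are needed at the initial step: with the new starting dose and with the new maximum.

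| Fall in CrCl (mL/min) | Initial rate ÷ new starting dose | Initial rate ÷ new maximum | Titration rate ÷ new maximum |
|---|---|---|---|
| >50 to 41–50 | 0.75/0.5 = 1.5 | 0.75/0.75 = 1 | 1.25/0.75 = 1.67 |
| 41–50 to 31–40 | 0.5/0.375 = 1.33 | 0.5/0.5 = 1 | 0.75/0.5 = 1.5 |
| 31–40 to 21–30 | 0.375/0.25 = 1.5 | 0.375/0.375 = 1 | 0.5/0.375 = 1.33 |
| >50 to 31–40 | 0.75/0.375 = 2 | 0.75/0.5 = 1.5 | 1.25/0.5 = 2.5 |
| 41–50 to 21–30 | 0.5/0.25 = 2 | 0.5/0.375 = 1.33 | 0.75/0.375 = 2 |
| >50 to 21–30 | 0.75/0.25 = 3 | 0.75/0.375 = 2 | 1.25/0.375 = 3.33 |

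- At the initial step, a one-band fall gives 1.33 to 1.5 times the new starting dose, but exactly the new band's titration dose. Table 1's maximum is not exceeded.
- At the initial step, a fall of two or more bands gives 1.33 to 2 times the maximum.
- At titration, every fall exceeds the maximum: 1.33 to 1.67 times for one band, up to 3.33 times for three.
- If CrCl has fallen below 21, Table 1 has no rate to compare with.

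**Age of the value.** Assume that CrCl was measured on admission on the day of the haemorrhage and that the infusion starts on the day of onset, day 4 to 14. The wording permits this without prescribing it; a later admission or measurement shortens these ages.

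- At initiation: 4 to 14 days.
- At titration, 24 hours later: 5 to 15 days.
- At a restart after one complete course of minimum length, CrCl above 50: an untitrated course takes 72 + 24 + 24 = 120 h = 5 days; a titrated one takes 24 + 72 + 4 × 24 = 192 h = 8 days. The age is then 4 + 5 = 9 to 14 + 8 = 22 days.

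**The case against.** The best counter-argument is that renal eligibility is looked at again when vasospasm is diagnosed, that restarting the protocol can be read as repeating that step, and that creatinine may well be measured in routine care. This helps only in part. The review needs no new result, so the admission value still satisfies it, and it is placed at diagnosis, not at the 24-hour titration. A clinician may act on a routine result, but no visible text links one to the dose.

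General safeguards also exist. At the provider's discretion, "any patients with dangerously low blood pressure, or other symptoms of shock, will have milrinone/placebo discontinued". Section 6.3 has the data safety monitoring board review adverse events, and section 7.0 lets the investigators withdraw a patient for safety. These limit harm once it shows; none directs a dose change when CrCl falls.

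Three objections stand. Figure 1 and the pharmacy orders mentioned in section 4.0 are not available, so a re-check there cannot be ruled out, although the explicit text of section 5.1 asks for none. Appendix A is a data list, so its single CrCl item does not prove that CrCl is measured only once. And patients on saline cannot be overdosed with milrinone, so the exposure is confined to one arm.

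A reader might go further and infer that any fall in CrCl leads to a rate Table 1 forbids. It does not: after a one-band fall the initial rate is one that the new band allows at titration. A reader might also infer that repeated courses breach a nine-day limit on infusion. Section 1.0 reports nine days as the longest experience at another centre and sets no limit. It does not say whether those days were continuous, so it shows no defect in the restart rule.

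**Conclusion.** The point holds as a dosing-safety gap. Following section 5.1 to the letter can put a patient in the milrinone arm above Table 1's maximum for current renal function: at titration after a fall of one or more bands, and at the initial rate after a fall of two or more. In the clearest case, a patient whose CrCl was above 50 goes to 1.25 mcg/kg/min when Table 1 would now set 0.75, 0.5 or 0.375.

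The standard used is the plan's own table; no outside pharmacology enters. The ratios are exact, but they apply only if CrCl has fallen since it was measured. The documents do not say how often that happens, so no expected number of affected patients can be given, and the 3.33-fold case should be read as an upper end. That 1.25 lies above the approved maximum of 1.13 is a choice the plan states and defends; the fault is only that an outdated CrCl can lead to it.

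No effect on sample size, power or the primary comparison is claimed, and none follows from the documents. Within those limits this is a cheap improvement worth making.

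**What to change.** In section 5.1, replace the wording on CrCl timing with:

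> CrCl is taken from a result within 24 hours before study drug initiation and within 24 hours before any titration or restart (a routine-care result suffices). Doses follow the Table 1 band for the most recent value; if the current rate exceeds the dose for that band and step, it is reduced. Study drug is not initiated, titrated or restarted, and a running infusion is stopped, if CrCl is below 21 mL/min (the lowest Table 1 band).

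The limit of 21 also settles a small mismatch: section 3.1 excludes only values below 20, while Table 1 has no dose below 21. In Appendix A, add the date, CrCl and rate at each titration or restart.

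The cost is one routine creatinine where no result from the previous 24 hours exists, and three data fields per titration or restart. Waiting for a result before the first dose may press on the target of delivery within two hours. A patient who has not improved and whose CrCl has fallen from above 50 would receive 0.75, 0.5 or 0.375 at titration in place of 1.25, as Table 1 intends. The text does not schedule a re-check during an infusion that is neither titrated nor restarted; there it acts only on results that routine care supplies. Sample size, blinding and analysis are unchanged.

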6.1.1 Adverse Event (AE)

An adverse event is defined as any unintended or abnormal clinical observation that is not of benefit to the patient. Either the condition was not present prior to study intervention, or it has worsened in intensity or frequency following study intervention. Adverse events will be graded according to the NCI Common Toxicity Criteria, Version 4.0 and will be logged for all patients in both arms of the study. The following grading scale will be used:

0 = No adverse event or within normal limits

1 = Mild adverse event

2 = Moderate adverse event

3 = Severe and undesirable adverse event

4 = Life-threatening or disabling adverse event

5 = Death related to adverse event

6.1.2 Serious Adverse Event (SAE)

A serious adverse event is any untoward medical occurrence resulting in one or more of the following:

- Results in death or ANY death occurring within 28 days of last dose of study drug (even if it is not felt to be drug related)
- Is life-threatening (defined as an event in which the patient was at risk of death at the time of the event; it does not refer to an event which hypothetically might have caused death if it were more severe)
- Requires inpatient hospitalization or prolongation of existing hospitalization

NOTE: Hospitalizations that are not considered SAEs are:

- Hospitalization planned prior to first administration of study drug

- Hospitalization for elective treatment of a pre-existing condition unrelated to the study medication
- Results in persistent or significant disability/incapacity
- Is a congenital anomaly or birth defect
- Is an important medical event (defined as a medical event(s) that may not be immediately life-threatening or result in death or hospitalization but, based upon appropriate medical and scientific judgment, may jeopardize the patient or may require intervention (e.g., medical, surgical) to prevent one of the other serious outcomes listed in the definition above). Examples of such events include, but are not limited to, intensive treatment in an emergency room or at home for allergic bronchospasm; blood dyscrasias or convulsions not resulting in hospitalization; or the development of drug dependency or drug abuse.

